#### **10.1.** General Considerations

All study data will be summarized by treatment group using descriptive statistics. Categorical variables will be reported using frequency and percentage (eg, gender, race). Continuous variables will be reported using number of patients, mean, standard deviation (SD), median, minimum, and maximum. All efficacy and safety data will be listed by subject.

## **10.2.** Determination of Sample Size

It is assumed that the proportion of subjects who achieve PGA score of clear (0) or almost clear (1) with a minimum 2-grade improvement from Baseline at Week 12 will be 40% for subjects receiving tapinarof compared with 15% for subjects receiving vehicle control. With 500 subjects randomized in a 2:1 ratio (approximately 333 subjects receiving tapinarof cream, 1% and approximately 167 subjects receiving vehicle cream) there will be > 99% power for a statistical significance (2-sided p< 0.05). If tapinarof response rate is 35%, and vehicle response rate is 20%, the power will be > 94%. The power is calculated from a Fisher Exact sample size calculation which is conservative. It is assumed that up to 25% of the subjects will be lost to follow-up by 12 weeks. These subjects will be included in the primary analysis using the multiple imputation method.

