#### **Statistical Methods:**

Determination of Sample Size: It is assumed that the proportion of subjects who achieve PGA score of clear (0) or almost clear (1) with a minimum 2-grade improvement from Baseline at Week 12 will be 40% for subjects receiving tapinarof cream, 1% compared with 15% for subjects receiving vehicle control cream. With 500 subjects randomized in a 2:1 ratio (approximately 333 subjects receiving tapinarof cream, 1% and approximately 167 subjects receiving vehicle cream), there will be > 99% power for a statistical significance (2-sided p< 0.05). If the tapinarof response rate is 35%, and the vehicle response rate is 20%, the power will be > 94%. The power is calculated from a Fisher Exact sample size calculation which is conservative. It is assumed that up to 25% of the subjects will be lost to follow-up by 12 weeks. These subjects will be included in the primary analysis using the multiple imputation method.

Efficacy Analyses: All efficacy analyses will be based on the Intent-to-Treat (ITT) population and will be repeated for the Per Protocol (PP) population only for the primary and secondary efficacy endpoints as supportive analysis. The primary efficacy endpoint will be analyzed using a Cochran–Mantel–Haenszel (CMH) test stratified by PGA score at Baseline (PGA scores of 2, 3, or 4). The same method used for the primary analyses will be used to analyze all dichotomized secondary endpoints. The secondary endpoints will be tested sequentially in order, and testing will stop if non-significance (2-sided  $p \ge 0.05$ ) is observed. Other efficacy endpoints will be analyzed

using CMH test for proportions, and analysis of covariance (ANCOVA) model for continuous variables. CMH tests will be stratified by baseline PGA score, and ANCOVA models will include PGA score as a covariate. Open-label data will be summarized using summary statistics without testing.

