### 4.6. Withdrawal Criteria

A subject may voluntarily discontinue treatment and/or withdraw from participation in this study at any time at his/her own request, or may be discontinued from study treatment at any time at the discretion of the Investigator for safety, behavioral, compliance, or administrative reasons. Subjects withdrawn from the study will not be replaced.

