### 7. SAMPLE SIZE DETERMINATION

It is assumed that the proportion of subjects who achieve PGA score of clear (0) or almost clear (1) with a minimum 2-grade improvement from Baseline at Week 12 will be 40% for subjects receiving tapinarof compared with 15% for subjects receiving vehicle control. With 500 subjects randomized in a 2:1 ratio (approximately 333 subjects receiving tapinarof cream, 1% and approximately 167 subjects receiving vehicle cream) there will be > 99% power for statistical significance (2-sided p< 0.05). If tapinarof response rate is 35%, and vehicle response rate is 20%, the power will be > 94%. Power comes from a Fisher Exact sample size calculation which is conservative. It is assumed that up to 25% of the subjects will be lost to follow-up by 12 weeks. These subjects will be included in the primary analysis in the ITT population using the multiple imputation method as detailed below.

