### Imputation of Missing Efficacy Data

The primary method of handling of missing efficacy data will utilize Multiple Imputations (MI). Last observation carried forward (LOCF) method will be used as supportive analysis of the primary and secondary endpoints. For sensitivity analysis of the primary and secondary endpoints, missing data will be imputed as Treatment Failures (TF). Only missing data up to Week 12 will be imputed. Missing data at the Week 16 Follow-up visit will be analyzed as Observed Cases (OC) only.

MI: For the MI model, 100 imputations will be generated using PROC MI of SAS. Fully Conditional Specification (FCS) model using the regression method will be used with the response (e.g., PGA score) at prior post-baseline visits, baseline PGA score, baseline value of the corresponding endpoint, and treatment group as covariates, The ROUND and MINIMUM options will be utilized to ensure imputed values are non-negative integers. The seed to be used in all MI model is 20180330.

One set of MI datasets will be generated for the PGA scores, PASI scores and %BSA results separately. Response status (Yes, No) will be derived from the imputed scores in each MI dataset. Analysis of each primary, secondary and exploratory outcome will then be performed for each of the relevant MI datasets. The results of the 100 analyses will be transformed into a normal statistic and combined into a single analysis using PROC MIANALYZE.

Example SAS code for the PGA scores is as follows:

```
PROC MI DATA = PGA1 OUT = PGA2 SEED = 20180330 NIMPUTE = 100 NOPRINT;
CLASS TRTPN BASEPGA;
FCS LOGISTIC(BASEPGA = TRTPN / DETAILS);
FCS REG(PGA3 = TRTPN BASEPGA / DETAILS);
FCS REG(PGA4 = TRTPN BASEPGA PGA3 / DETAILS);
FCS REG(PGA5 = TRTPN BASEPGA PGA3 PGA4 / DETAILS);
FCS REG(PGA6 = TRTPN BASEPGA PGA3 PGA4 PGA5 / DETAILS);
VAR TRTPN BASEPGA PGA3-PGA6;
RUN:
```

The imputation models may be modified based on the actual data if there is an issue in model convergence.

**LOCF:** The last observed value will be carried forward for any subsequent missing values. Baseline values will not be carried forward.

**TF**: missing data will be imputed as treatment failures for responder endpoint.

Missing functional outcomes, quality of life endpoints or safety endpoints will not be imputed.

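### The >94% power at 35% vs 20% holds only if every Week 12 outcome is observed; at the plan's own 25% loss ceiling its Fisher method gives about 85% on observed outcomes

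*Protocol*

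**What the plan says.** Protocol 10.2 plans 500 randomized subjects in a 2:1 ratio, about 333 on tapinarof and 167 on vehicle, tested at two-sided 0.05. The main case is a 40% vs 15% response, with stated power above 99%. For the weaker case it says "If tapinarof response rate is 35%, and vehicle response rate is 20%, the power will be > 94" percent, and on method, "The power is calculated from a Fisher Exact sample size calculation which is conservative". The next two sentences concern missing outcomes: "It is assumed that up to 25% of the subjects will be lost to follow-up by 12 weeks", and then "These subjects will be included in the primary analysis using the multiple imputation method".

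The synopsis (Statistical Methods) carries the same claim: "If the tapinarof response rate is 35%, and the vehicle response rate is 20%, the power will be > 94" percent. SAP section 7 repeats the whole paragraph and ends "These subjects will be included in the primary analysis in the ITT population using the multiple imputation method as detailed below". Protocol 4.6 adds "Subjects withdrawn from the study will not be replaced".

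Under SAP 12.8 and 12.8.1, the primary analysis is intent-to-treat with multiple imputation. In each imputed dataset a log relative risk stratified by baseline PGA is estimated, and the results are combined across imputations. Observed-case, treatment-failure and last-observation-carried-forward analyses are sensitivity or supportive analyses.

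**The concern.** A reader who meets >94% beside an assumed loss of up to 25% will take it that the power allows for the loss. Nothing in the paragraph says otherwise, and the remarks on conservatism and imputation encourage that reading. If the figure was computed on all randomized subjects with complete outcomes, the plan's stated robustness to weaker response rates is overstated under its own missing-data assumption. At stake is the accuracy of the stated type II error in the weaker scenario of a pivotal trial, not the validity of the primary test.

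**Working it through.** **Inputs** (Protocol 10.2): two-sided alpha 0.05; about 333 and 167 subjects; response rates 35% vs 20% (secondary case) and 40% vs 15% (main case); Fisher exact test; loss up to 25%. The documents do not split the loss by arm. I assume it is equal.

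**Formula.** With a ~ Bin(n1, p1) and b ~ Bin(n2, p2), power is the sum over all (a, b) of P(a)·P(b) for which the two-sided Fisher p-value is below 0.05. This was evaluated by full enumeration.

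**Reproducing the plan's figure, no loss, 35% vs 20%.** 333/167 gives 93.8% and 334/167 gives 94.05%. The claim of >94% is therefore reproduced to rounding. At 40% vs 15%, power exceeds 99.99%, in line with the stated >99%.

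**Allowing for loss.** At 25%, 333 × 0.75 ≈ 250 and 167 × 0.75 ≈ 125, so 375 outcomes are observed. For 35% vs 20%:

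| Loss | Observed n | Fisher power | Type II error |
|---|---|---|---|
| 0% | 333/167 | 93.8% | 6.2% |
| 5% | 316/159 | 93.0% | 7.0% |
| 10% | 300/150 | 91.5% | 8.5% |
| 14% | 286/144 | 89.9% | 10.1% |
| 20% | 266/134 | 87.8% | 12.2% |
| 25% | 250/125 | 85.3% | 14.7% |

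Fisher power moves in small steps: 249/125 gives 84.9% and 250/126 gives 86.0%, so about 85% is the right precision. At 40% vs 15% with 250/125, power is 99.9%.

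**Hand check with the pooled z formula,** power = Φ[(d − 1.96·se0)/se1]:
- 333/167: pooled rate 0.2999, se0 = √(0.2999 × 0.7001 × (1/333 + 1/167)) = 0.0434, se1 = √(0.35 × 0.65/333 + 0.20 × 0.80/167) = 0.0405. Power = Φ(1.60) = 94.5%.
- 250/125: pooled rate 0.30, se0 = 0.0502, se1 = 0.0468. Power = Φ(1.10) = 86.5%.

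**Does Fisher's conservatism cover the gap?** A one-stratum Cochran–Mantel–Haenszel (CMH) test, also fully enumerated, gives 94.5% with no loss, 92.1% at 10% and 86.7% at 25%. Its gain over Fisher at 250/125 is 86.7 − 85.3 = 1.4 points. The drop due to loss under Fisher is 93.8 − 85.3 = 8.5 points.

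**Does imputation cover it?** The documents give no visit correlation, dropout timing or full PGA distribution, so no figure can be derived. Three illustrative simulations, with all inputs assumed and 25% loss completely at random and equal by arm, gave:
- Two outcome models with sequential normal regression, rounding, 100 imputations and pooling of the stratified logit log relative risk (1,000 trials per setting, Monte Carlo SE about 1 to 1.4 points): 85.5–90.0% against 92.5–93.5% with no loss, and 74.5–82.6% against 89.7–92.6%.
- A simpler, idealised one (one prior visit, no strata, imputation on an underlying continuous scale): 88.5–93.4% for latent correlations from 0 to 0.9, against 93.6% with no loss. Only the 0.9 setting matched the no-loss figure within simulation error.

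**Treatment-failure sensitivity analysis at 25% loss.** If 35% and 20% are rates among observed subjects, the effective rates are 0.35 × 0.75 = 26.25% and 0.20 × 0.75 = 15%, and Fisher at 333/167 gives 82.0%. If they already count missing as failure, there is no dilution.

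**The case against.** The strongest reply is that no stated number is wrong. Both powers reproduce, the arm sizes are printed in the preceding sentence, and the loss is disclosed together with how it will be handled. The primary analysis is multiple imputation on all randomized subjects, so 85% is the power of a sensitivity analysis and not of the primary test. Further, 25% is an upper bound. Early termination visits record a PGA (Protocol 7.5), and from Day 71 they map to Week 12 (SAP 11.4), so not every withdrawal is a missing outcome. The scenario is secondary, and power stays above 80%.

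Much of this stands. The 85% must be labelled as an observed-outcome figure. The trial is not underpowered, and the main case is untouched. The simulations disagree on level, and part of the shortfall in the lower set comes from the logit relative-risk test itself, which is below 93% there even with no loss. They support no specific figure for the planned analysis.

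What does not stand is the inference that the loss is covered. Fisher on complete data is not the primary test either. It is the plan's chosen yardstick, and applying it to the plan's own loss assumption is like for like. Keeping a subject in the denominator does not supply the unobserved outcome, and the combining step adds between-imputation variance for that reason.

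**Conclusion.** The concern holds. The >94% is a complete-data figure presented beside a loss assumption that it does not reflect. At the 25% ceiling, the plan's own method gives about 85% on observed outcomes, with a type II error of about 15% rather than 6%. At 10% loss it gives 91.5%, and power first falls below 90% at about 14% loss. These enumerations are firm, given equal loss by arm and response rates that are the same in observed and lost subjects. Power under the planned imputation analysis is unknown from the documents. It should be corrected, but it is a flaw in the justification: 40% vs 15% keeps 99.9% power at 25% loss.

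**What to change.** Keep 500 subjects and the planned analysis. In the synopsis, Protocol 10.2 and SAP section 7, replace the secondary-scenario sentence with wording such as: *At 35% vs 20%, Fisher exact power is about 94% when all Week 12 outcomes are observed; based on observed outcomes alone it is about 91.5% with 10% missing and about 85% with 25% missing. Multiple imputation is not assumed to recover the complete-data power.* Give a power figure for the imputation analysis only if the sponsor simulates it and states the visit correlations, dropout timing and PGA distribution used.

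The cost is a wording change in three places and a less favourable figure for the secondary scenario. No extra subjects are needed and no analysis changes.

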## 10.3. Analysis Populations

#### 10.3.1. Safety

All randomized subjects who receive at least 1 application of study drug will be included in the Safety population. Subjects will be analyzed as treated.

#### 10.3.2. Intent-To-Treat

All randomized subjects will be included in the Intent-to-treat (ITT) population. Subjects will be analyzed as randomized.

#### 10.3.3. Per-Protocol

All subjects in the ITT population who did not have any major protocol deviations will be included in the Per Protocol (PP) population. Subjects will be analyzed as treated.

#### 10.3.4. Pharmacokinetic

All subjects who undergo plasma PK sampling and have evaluable concentration-time data for analysis will be included in the PK population. A sample that is below the limit of quantification (BLQ) of the assay is considered evaluable.

## 10.4. Planned Analyses

All efficacy and safety measures over the course of the study will be presented. Details of planned analyses will be described in the Statistical Analysis Plan (SAP), which will be finalized prior to database lock.

#### **10.4.1.** Disposition and Demographics

Demographic and baseline characteristics as well as medical history will be summarized using the ITT population, including frequency and percentages for categorical variables and mean, standard deviation, median, minimum, and maximum for continuous variables.

The numbers of subjects in the different analysis populations will be summarized by treatment group, including overall categories.

#### 10.4.2. Efficacy Analyses

All efficacy analyses will be based on the ITT population and will be repeated for the PP population only for the primary and secondary efficacy endpoints as supportive analysis.

#### 10.4.2.1. Primary Endpoint Analyses

The primary efficacy endpoint is proportion of subjects who achieve PGA score of clear (0) or almost clear (1) with a minimum 2-grade improvement from Baseline at Week 12. The primary efficacy endpoint will be analyzed using a Cochran–Mantel–Haenszel (CMH) test stratified by PGA score at Baseline (PGA scores of 2, 3 or 4).

#### 10.4.2.2. Secondary and Exploratory Efficacy Endpoint Analyses

The secondary efficacy endpoints are as follows:

- Proportion of subjects with ≥ 75% improvement in PASI from Baseline at Week 12
- Mean change in %BSA affected from Baseline to Week 12
- Proportion of subjects with a PGA score of 0 or 1 at Week 12
- Proportion of subjects with ≥90% improvement in PASI score from Baseline to Week 12

Exploratory efficacy endpoints are as follows:

- Time to achieve a PGA score of 0 or 1 with a minimum 2-grade improvement from Baseline
- Proportion of subjects with a PGA score of 0 or 1 at Weeks 2, 4, and 8
- Proportion of subjects who achieve a PGA score of 0 or 1 with a minimum 2-grade improvement from Baseline at Weeks 2, 4, and 8
- Mean absolute and percent change in PASI score from Baseline to Weeks 2, 4, 8, and 12
- Proportion of subjects with ≥ 50% improvement in PASI score from Baseline to Weeks 2, 4, 8, and 12
- Proportion of subjects with ≥ 75% improvement in PASI score from Baseline to Weeks 2, 4, and 8

- Proportion of subjects with ≥ 90% improvement in PASI score from Baseline to Weeks 2, 4, and 8
- Mean change in %BSA affected from Baseline to Weeks 2, 4, and 8

The same methods as discussed for the primary analyses will be used to analyze all dichotomized secondary endpoints. The secondary efficacy endpoints will be tested sequentially in the order listed. Testing will stop if non-significance (2-sided  $p \ge 0.05$ ) is observed.

Other efficacy endpoints will be analyzed using CMH test for proportions, and analysis of covariance (ANCOVA) model for continuous variables. CMH tests will be stratified by baseline PGA score, and ANCOVA models will include PGA score as a covariate.

All endpoints will be summarized descriptively as follows: continuous data will include the mean, SD, minimum, maximum, median, and number of observations; descriptive summary statistics for categorical data will include frequency counts and percentages.

#### 10.4.3. Safety Analyses

The Safety Population will be used in the analysis of safety data. Data will be listed by subject and treatment and summarized by treatment. No formal statistical comparisons will be made for safety data.

The number and proportion of subjects with TEAEs will be summarized by treatment, system organ class, and preferred term for all TEAEs, all TEAEs considered by the Investigator to be related to study drug, all SAEs, and all TEAEs leading to study drug discontinuation. Summaries of AEs will be presented separately for double-blind and open-label treatment phases. All AE summaries will include information for AEs that occurred after administration of the first dose of study drug until completion of the final study visit. Data listings will be provided for subjects who discontinued the study due to an AE and for subjects with an SAE.

Selected laboratory data will be analyzed using descriptive summary statistics and will be presented by study visit and treatment group, including the number of non-missing observations, mean and SD, median, upper and lower quartiles, minimum and maximum for values and changes from Baseline. Categorical safety data will be analyzed using frequency tables and, if applicable, shift tables.

Vital signs will be listed by subject and summarized by visit.

Mean scores from the LTS will be summarized by visit.

#### 10.4.4. Analysis of Functional Outcomes and Quality of Life Endpoints

The subject-reported endpoints to examine the effect of study drug on psoriasis symptom severity and the associated impact on daily activities and attitudes are as follows:

- Change in Peak Pruritus-NRS from Baseline at Weeks 2, 4, 8, and 12
- Change over time in psoriasis impact on daily activities, as measured by the DLQI total and individual dimension scores
- Change over time in psoriasis symptoms, as measured by the PSD
- Change over time in physical component score and mental component score, as measured by the SF-36 questionnaire

Change from baseline in DLQI, PSD, SF-36, and Peak Pruritus-NRS scores will be analyzed using an ANCOVA model with treatment as a main effect, and baseline as a covariate.

#### 10.4.5. Pharmacokinetic Analyses

Data will be listed and summarized. Listings will be sorted by subject, day, and time; summaries will be presented by study visit and time from last dose.

Unless stated otherwise, descriptive summaries for continuous variables will include n, mean, SD, median, minimum, and maximum. If data permit, time to steady state will be assessed using the sampled trough values. Exploratory analyses may include relationships of plasma concentrations with patient demographics or AEs.

## 10.5. Interim Analyses

No interim analyses will be performed from a statistical standpoint.

## 10.6. Handling of Missing Data

Every effort will be made to collect complete data at all visits.

The primary method of handling of missing data will utilize Multiple Imputations (MI). For sensitivity analysis, Treatment Failure (TF) will be imputed for missing data.

For the MI model, 100 imputations will be generated using PROC MI of SAS. Fully Conditional Specification (FCS) model using the regression method will be used with the response (eg, PGA score) at prior post-baseline visits, baseline strata, and treatment group as covariates, The ROUND and MINIMUM options will be utilized to ensure imputed values are non-negative integers. The seed to be used is 20180330. The results of the 100 analyses will be transformed into a normal statistic and combined into a single analysis using PROC MIANALYZE.

#### Clinical Study Protocol - Version 2.0

#### 11. RESPONSIBILITIES

## 11.1. Investigator Responsibilities

#### 11.1.1. Good Clinical Practice

The Investigator will ensure that this study is conducted in accordance with the principles of the "Declaration of Helsinki" (as amended in Edinburgh, Tokyo, Venice, Hong Kong, and South Africa), International Conference on Harmonization (ICH) guidelines, or with the laws and regulations of the country in which the research is conducted, whichever affords the greater protection to the study subject. For studies conducted under a United States Investigational New Drug Application (IND), the Investigator will ensure that the basic principles of "Good Clinical Practice," as outlined in 21 Code of Federal Regulations (CFR) 312, subpart D, "Responsibilities of Sponsors and Investigators," 21 CFR, part 50, 1998, and 21 CFR, part 56, 1998, are adhered to. These standards are consistent with the requirements of the European Community Directive 2001/20/EC.

Since this is a "covered" clinical trial, the Investigator will ensure that 21 CFR, Part 54, 1998, is adhered to; a "covered" clinical trial is any "study of a drug or device in humans submitted in a marketing application or reclassification petition subject to this part that the applicant or Food and Drug Administration (FDA) relies on to establish that the product is effective (including studies that show equivalence to an effective product) or that make a significant contribution to the demonstration of safety." This requires that Investigators and all sub-investigators must provide documentation of their financial interest or arrangements with the Sponsor, or proprietary interests in the drug being studied. This documentation must be provided before participation of the Investigator and any sub-investigator. The Investigator and sub-investigator agree to notify the Sponsor of any change reportable interests during the study and for 1 year following completion of the study. Study completion is defined as the date that the last subject has completed the protocol-defined activities.

